### Patient Focus Groups

We will conduct 3 focus groups, approximately 2 weeks apart, to elucidate acceptance and usability regarding the app and mobile monitoring. Each focus group will entail participants discussing perceived usefulness, ease of use, attitudes, self-efficacy, norms, facilitating conditions and behavioral intent. The focus groups will be co-led by the qualitative methods expert and research staff. Each focus group will include 6 Veterans who meet inclusion criteria. Focus groups will be digitally audio recorded and professionally transcribed.

### Patient In-Lab Usability Trials

After app modifications have been made in response to the focus groups and clinician interviews, in-lab usability trials will be conducted. The trials will be conducted in an office at the VA. They will be co-led by the qualitative methods expert and research staff. Users will participate individually and will be asked to complete specific tasks (e.g., find the dashboard of your sleep). Topics include downloading and opening the app, reviewing dashboards, closing the app, and managing the app on the user's phone. The user will be asked to verbalize their thoughts as they go through the experience of navigating the app. Research staff logs what the participant did and said in as much detail as possible. Errors are also counted (e.g., wrong pathways, failure to find content).

### Patient Participant Assessments and App Download

For participants in the mobile sensing trial, after the informed consent process, research staff administer the baseline research assessment. Then the project app is downloaded to the participant's

phone. It is activated by staff using a code. Each time the app is activated on a device, a unique ID is created by the server. This ID connects data from the app with patient identifiers kept on the secure server. After the app is activated, it runs in the background and collects data passively with no further action from the user.

Participants will receive phone calls from study staff on a weekly basis throughout a 9-month study period to complete assessments by phone. Based on our experience with these assessment instruments, as staff get to know individual patients the time required for assessments becomes relatively brief. A semi-structured qualitative interview will also be conducted at 3 months by phone with a subsample of participants until data saturation is achieved. At the conclusion of the 9 month study period, the participants meet with research staff for a final follow-up interview. At this point, the project app will be deleted from the phone, and the participant will be notified that it is no longer functional. The final assessment will also include a qualitative component for a subsample of participants until data saturation is achieved.

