#### Patient Participant Eligibility

The study involves distinct patient samples: participants in 3 focus groups (n=6 each), participants in an individual in-lab usability trial (n=8), and users of the app for 9 months (n=100). The inclusion and exclusion criteria are the same for all samples, as are the recruitment methods. An individual can participate in one focus group, an in-lab usability trial, and the mobile sensing trial. Furthermore, individuals can participate in the in-lab usability trials or mobile sensing trial and not have participated in the focus groups.

Inclusion criteria: 1) chart diagnosis of SMI, defined as a diagnosis of schizophrenia, schizoaffective disorder, or bipolar disorder, confirmed by the patient's treating psychiatrist; 2) risk for symptoms based on having had, during the past year, psychiatric hospitalization, psychiatric emergency care, lived at a crisis treatment program, or more than 6 outpatient treatment visits; and, 3) ownership of a phone with a data plan.

Exclusion criteria: 1) under age 18. 2) Patient has a conservator/legally authorized representative who makes their medical decisions.

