Using multivariate analyses, we study whether quantitative baseline patient characteristics described above are associated with feasibility, acceptability, and safety. Qualitative data from patients 3-month and 9-month interviews are used to evaluate themes related to the feasibility, acceptability and safety of sensing. Qualitative data from post-intervention clinician interviews are used to evaluate themes related to patient engagement, findings, implementation, and resources for sustainability and incorporation into routine practice. Using ATLAS.ti, transcripts of interviews will be coded deductively for major subthemes regarding acceptability, strengths and weaknesses, barriers and facilitators of use, safety, and recommendations about future revisions and implementation efforts. The qualitative findings will be triangulated with findings from the other measure of acceptability and safety to examine whether concordance exists among these measures of the intervention. Should analytic anomalies in the quantitative findings arise, the qualitative data will be explored to illuminate possible explanations for unexpected findings. At 3 and 9 months, 26 individuals should be sufficient to provide data saturation regarding acceptability of the intervention using qualitative data.

Aims 3 & 4. Use mobile sensor and phone utilization data to develop individualized estimates of sociability, activities, and sleep as measured by weekly interview. Study the predictive value of using data on sociability, activities, and sleep to identify exacerbations of psychiatric symptoms.

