generalization error. Quadratic loss will be used to evaluate prediction error. The selected model will be the one that minimizes LOOCV mean squared error.

In Aim 4, outcome data are collected weekly for each patient on three scales (psychosis, mania, depression). These scales each have a range of 1 to 7. The primary outcome will be the scale indicating the most severe symptoms in a 2-month window. We will evaluate the association between mobile data features identified in Aim 3 with this primary outcome using a mixed effects model to accommodate within patient data correlation due to repeated measures. Specifically, we will consider feature data from fixed time windows preceding the most severe symptoms. The outcome data distribution will be examined prior to model fitting, and an appropriate link function will be used in the mixed effects model.

Sample size and power considerations: In Aim 3, we extract features of mobile sensor and phone utilization data to estimate behaviors in the domains of sociability, activity, and sleep. The selected features should have a high correlation with behaviors to be a good estimate. Of 100 participants enrolled, assuming 30% attrition, we expect to have complete data on 70 participants (and substantial longitudinal data for a larger group). This sample size will provide over 95% power to detect a correlation of at least 0.50 at the significance level 0.05 using a two-sided test. In Aim 4, our inclusion criteria select for greater than average symptom risk, so we anticipate substantial symptoms. Previous research on 21 patients with SMI for a median of 134 days found that sensing data predicted symptom indicator scores with correlations in the range of 0.5 to 0.8. Given possible confounders, and since our sample may be more heterogeneous than prior research, the correlation in our study is anticipated to be lower than what was reported previously. With 100 enrolled, and assuming 30% attrition, we will have over 85% power to detect correlations of at least 0.35 between predictors of interest and symptoms assessments at the significance level of 0.05 using a two-sided test.

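### As written, the 9-month interviews reach only those who attend the final visit, and the plan collects no reasons from participants who stop earlier

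*Combined protocol and SAP*

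**What the plan says.** The section Patient Participant Assessments and App Download sets the timing of the last contact: "At the conclusion of the 9 month study period, the participants meet with research staff for a final follow-up interview". It then attaches the qualitative interview to that contact: "The final assessment will also include a qualitative component for a subsample of participants until data saturation is achieved". The same section plans a 3-month interview by phone, also in a subsample and also run to saturation.

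The Methods section describes the mode in two ways. Its account of the mobile sensing trial has the 3-month interview by phone and the 9-month interview in person. A later paragraph brings participants to the VA for the final quantitative interview but describes both qualitative interviews as held by phone.

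Formative evaluation assessments gives the interview content (likes and dislikes and the reasons for them, perceived usefulness, recommendations) and adds a monthly count, per participant, of days on which the app recorded and transmitted. Under Aims 1 & 2, Data Analyses defines acceptability by days of use together with the interviews, codes transcripts for barriers and facilitators among other themes, and compares the qualitative findings with the other measures. On numbers it says: "At 3 and 9 months, 26 individuals should be sufficient to provide data saturation regarding acceptability of the intervention using qualitative data".

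The sample-size paragraph plans for loss: "assuming 30% attrition, we expect to have complete data on 70 participants".

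The documents contain no exit interview, no planned record of reasons for leaving, and no rule for choosing either interview subsample.

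**The concern.** Acceptability is a stated objective under Aim 2, and the interviews are the part of the plan meant to explain why participants do or do not use the app. People who stopped are the most direct source on that question. An interview held at the final visit does not reach someone who withdrew and does not come back. Saturation is the rule for ending recruitment to the interviews, but saturation among attenders says little about the reasons of those who left.

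The plan also intends to turn to the qualitative data when the quantitative findings are puzzling. If the usage counts show that some participants stopped early, the 9-month interviews, drawn from attenders, are poorly placed to say why.

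**Working it through.** **Inputs.** From the documents: 100 enrolled, 30% attrition, 26 interviewees. Assumed, because the documents do not say: 26 applies at each time point; all 30 participants without complete data are leavers; the 3-month sample is drawn at random from those still enrolled.

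**The plan's own figure.** 100 × (1 − 0.30) = 70 with complete data, which reproduces the stated number. The power statements built on it concern correlations in Aims 3 and 4 and do not use the interviews, so power is unaffected.

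**Who can be reached at 9 months.** Since the qualitative component belongs to the final assessment, and that assessment closes the 9-month period, only attenders can be sampled. If leavers do not attend, the expected number among the 26 is 0. This follows from timing and place; the plan states no rule restricting interviews to completers.

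**Proportional share of leavers in 26.**
- At 30% leaving: 26 × 0.30 = 7.8, about 8.
- At 15% leaving (assumed, half the planning figure): 26 × 0.15 = 3.9, about 4.

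**What the 3-month interviews can recover.** Let G of the 30 leavers be gone by month 3. Then N = 100 − G remain, of whom L = 30 − G leave later. The expected number of later leavers in the sample is 26 × L / N. The chance of including none is C(70, 26) / C(N, 26), because N − L = 70 throughout.

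| Gone by month 3 (G) | Later leavers / still enrolled | Expected in 26 | Chance of none |
|---|---|---|---|
| 0 | 30 / 100 | 7.8 | 0.00002 |
| 10 | 20 / 90 | 5.8 | 0.0004 |
| 15 | 15 / 85 | 4.6 | 0.002 |
| 22 | 8 / 78 | 2.7 | 0.03 |

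Under random sampling, then, the 3-month interviews would almost certainly include some people who leave later. They are heard while still participating, so their reasons for stopping are not captured, and the G people already gone are in neither interview round. The protocol states no sampling rule, so even this degree of coverage is not assured.

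**What the counts recover.** Days of recording are tallied for each participant, so stopping appears in the acceptability result. The tally shows that use ended, not why.

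**The case against.** The strongest counter-argument is that the plan does not depend on the 9-month interviews alone. Days of use cover everyone, feasibility includes continued involvement, the 3-month interviews address the same topics, and comparison across measures is a check on one-sided themes. All of that stands, and it rules out several stronger readings that a reader might infer.

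- *That leavers' views are missing from the acceptability result altogether.* They are not: usage is counted for all, and the table shows that later leavers are likely to be heard at 3 months.
- *That the views of 30 people are lost.* The 30% is a planning assumption for complete data in the power statement, and the plan expects substantial longitudinal data on a group larger than 70. Someone who removed the app or skipped weekly calls could still attend the final visit.
- *That the overstatement can be given as a percentage.* If a proportion were reported, it would be the leaving share times the difference between completers and leavers: 0.30 × 20 = 6 points, or 0.30 × 50 = 15. But those differences are invented, and the plan reports coded themes, not a proportion finding the app acceptable.
- *That safety is compromised in the same way.* Safety is measured by the rate of serious adverse events, with adverse events monitored through weekly calls and the medical record. It does not rest on these interviews.

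What the counter-argument leaves untouched is that no planned contact asks a person who has stopped why they stopped.

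**Conclusion.** The point holds in a limited form. As written, the end-of-study interviews are confined to attenders of the final visit, and the plan has no other route to the views of those who leave before month 3 or to the post-exit views and reasons of later leavers. The likely effect is a tilt of the 9-month acceptability and barrier themes toward favourable views. The direction is plausible; the size is unknown and cannot be derived from the documents.

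The figure of 4 to 8 interviews indicates scale only. It rests on 15% to 30% leaving and on 26 interviews at a time point. This is a worthwhile low-cost improvement to one part of an Aim 2 outcome, not a defect that invalidates the aim. It is best made before enrolment, because reasons for leaving are hard to recover afterwards.

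**What to change.** Amend the protocol as follows.

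- Within the planned interviews (about 26), purposively reserve some, for example 4 to 8, for participants who withdraw, remove the app or stop the weekly calls. Offer these by phone at the time the person stops, where consent allows.
- Record the reason for leaving, where given, for everyone who stops.
- State how both interview subsamples are chosen, and whether 26 applies to each time point.
- Report themes by completion status. Do not claim separate saturation among leavers: nothing in the documents supports saturation in a group that small.
- Reconcile the Methods paragraph that has the 9-month interview by phone with the other Methods paragraph and the assessment section, which put it in person or at the final meeting. The mode affects who can be reached.

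The number of interviews and staff need not change, since staff already call participants weekly and interview by phone at 3 months. The costs are that some leavers will decline and that fewer completers are interviewed: 26 − 4 = 22 down to 26 − 8 = 18. Contact after withdrawal must be covered by the consent form, which could not be checked here.

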## Study Measures

### Screening

Demographic and Psychiatric: VistA data, extracted by a study analyst, will be used to obtain psychiatric diagnosis and age. VistA data will be used to identify whether the individual has received treatment from GLA VA during the past year and is at high risk for symptoms as defined in the inclusion criteria.

Phone Ownership and Data Plan: We will ask to see the potential participant's cell phone to confirm cell phone platform type, and see a cell phone bill to confirm that they have a data plan.

### Baseline and Final Follow-up

Demographics: Demographic data including age, race, ethnicity, marital status, educational attainment, annual family income, and household roster; and psychiatric illness history will be collected from the patient at baseline only.

Phone data plan: Phone data plan information will be collected from each patient's recent phone bill brought to the baseline assessment. We will also collect their phone number.

Psychopathology, Substance Abuse, Cognitive Deficits, Functioning: Psychopathology will be measured using the Brief Psychiatric Rating Scale (BPRS) at both baseline and 9 month follow-up. Psychopathology will be measured using the Brief Psychiatric Rating Scale (BPRS). We will use the BPRS Positive Symptoms Factor (psychosis), Activation Factor (mania), and Affect Factor (depression) (9 items total).

Cognitive deficits of SMI will be measured by brief assessment. We will assess verbal learning using the Hopkins Verbal Learning Test-Revised (HVLT-R), and processing speed using the Digit Symbol Coding Test at baseline only. Occupational, social, symptom-related and overall functioning will be assessed using the MIRECC GAF at baseline only, which has been validated in Veterans with SMI.

Housing Stability: Housing stability for the past 30 days will be assessed using the Residential Time-Line Follow-Back Inventory (RTLFB). The RTLFB has been used in prior research to collect retrospective housing history over a specified period of time among people who have experienced homelessness. All residences over 30 days will be recorded, and coded into one of 34 previously defined locations, which will be further categorized as "stable" (e.g., own apartment, room or studio apartment in a supportive housing program, transitional housing, group home, boarding home) versus "unstable" (e.g., living on the streets, in public places, in emergency shelter-type accommodations) settings, using established methodology. The number of days spent in any of the locations categorized as "stable" or "unstable" will be summed and divided by the total number of days of residency reported at the interview,

and reported as a percentage. RTLFB has been demonstrated sensitive to change. This will be collected at baseline only.

Medication Possession Ratio (MPR): MPR has been shown to be a valid measure of medication adherence in Veterans with SMI. MPR assesses the extent to which dispensed medications provide coverage for the given interval. We will calculate a MPR for the 12 months pre-baseline using pharmacy data to assess medication adherence.

Healthcare Utilization: The Service Use and Resources Form (SURF) will be completed by patients at baseline only. SURF has been successfully used to assess costs and service utilization in numerous multi-site studies with patients with SMI, including CATIE. For the present study, we will use the SURF questionnaire to collect information on inpatient and outpatient services utilization, including type of facility and type of clinician contact, for visits both inside and outside VA settings.

Sociability, Activity, Sleep and Symptoms: We will administer the measures for these 4 domains described below at both baseline and the follow-up.

#### *Weekly research assessments*

Sociability: Social withdrawal and functioning will be assessed using the Abbreviated Lubben Social Network Scale (6 items) and the Objective Frequency of Social Contact scale (6 items).

Activity: Physical activity, routines and habits will be assessed using the Short International Physical Activity Questionnaire (4 items) and the Independence Performance and Prosocial domains of the Social Functioning Scale (15 items).

Sleep: Sleep duration and quality will be assessed using components 1, 2, 3 and 6 from the Pittsburgh Sleep Quality Index (5 items) and the Insomnia Problem items from the Insomnia Severity Index (3 items).

Symptoms: Symptom severity will be assessed using the Brief Psychiatric Rating Scale. We will use the BPRS Positive Symptoms Factor (psychosis), Activation Factor (mania), and Affect Factor (depression) (9 items total).

Safety: We will monitor adverse events on a weekly basis using data from weekly assessment phone calls and the medical record. Based on prior research studies of mobile sensing in people with SMI, and our prior mobile informatics research in patients with SMI at VA, we do not expect any safety problems.

#### *Formative evaluation assessments*

Acceptability: At 3 and 9 months, a semi-structured interview will be conducted with a subsample of participants until data saturation is achieved. The interview will be audio recorded and professionally transcribed. The interview will assess acceptability of mobile sensing, including usefulness, ease of use, attitudes and behavioral intention towards use. We study what participants like and do not like and why, their perception of the usefulness of mobile sensing as a tool to improving their assessment and care, and their recommendations for program refinements. These interviews will be digitally recorded. Monthly, we will calculate the number of days that the app was recording and transmitting data for each participant.

Safety: We will monitor the rate of serious adverse events throughout participation.

#### *Data Collected from Mobile Application*

The app collects passive behavioral data for assessment in three domains that have previously been proven to be measurable using these data: sociability, activities, and sleep. Sensor data collected from the app is encrypted and cached locally on the device, securely transmitted to the platform's remote server when a data connection is available. Analyses will seek to correlate behavioral patterns with emotional well-being. Analyses will also conduct time-series analysis to monitor shifts over time. We

anticipate detecting acute health stress through shifts in behavior patterns. The app will passively collect behavior data in three domains: sociability, activity, and sleep.

Participants will be able to view the tracking of their activities, sociability and sleep over time, similar to how people currently view their step counts in mobile health app dashboards. Each of the behavioral domains in this project will be presented on a 1-100 scale, as numbers graphed over time.

Sociability explores social characteristics of the individual. Dynamic and active social lives are correlates of mental health. Concurrently, sudden changes in sociability, particularly a notable increase in introversion and isolation could be indicators of diminishing mental health. Sociability assesses social characteristics by collecting information on calls and texts made with the phone (the content of these communications is not assessed or recorded) and public interaction by measuring ambient sound in social environments. Specific measures of Sociability we will attempt to gather:

- Communication: regular communication with a diverse set of individuals by phone call, text messaging, or use of messaging apps
- Public Interaction: regular communication with others in person or spending time in a social environment

Activity measures an individual's day-to-day routine by monitoring activity, movement, location, and habits. Adhering to regular routines, engaging in exercise, and productive activity outside the home are indicators of mental health. Changes in routines, lack of exercise, and limited intentional movement outside the home can be signs of mental health issues. Specific measures of Activity we will gather:

- Routine: a regular and structured daily and weekly routine
- Exercise: regular exercise
- Activities: Engagement in activities, particularly outside of the individual's residence

Sleep measures will focus on regular, uninterrupted sleep, in sufficient quantities represents one of key measures of mental health. Sleep measures collect data on ambient light, ambient sound, phone movement, lack of communication, and lack of use of the phone. Specific measures of Sleep we will attempt to gather:

- Quality: Is the individual having uninterrupted sleep
- Duration: what is the length of sleep the individual is having

Table 1. Data for Modeling of Behavioral Domains

Behavioral Domain	Input Data from Phone	Model Output Classifiers
Activities physical activity intensity and duration (walking, running, climbing stairs, riding bicycle) vs. sedentary organized activities: number and duration outside the individual's residence regular structured activities throughout each day (location and duration)	
 
• accelerometer sensor: acceleration force data for three coordinate axes
 
• linear accelerometer Android software: acceleration force data for three coordinate axes (excludes gravity)
 
• gyroscope sensor: rotation data for three coordinate axes
 
• rotational vector Android software: rotation vectors for three coordinate axes and scalar
 
• step counter Android software
 
• significant motion Android software: motion leading to change in location
 
• Activity Recognition Google API: still, on foot, on a bicycle, in a vehicle
 
• Fused Location Google API (uses GPS & wifi): location after 5 meters of movement
 
	
 
• Short International Physical Activity Questionnaire (4 items)
 
• Independence, Performance and Prosocial domains of the Social Functioning Scale (15 items)
 

Sleep total sleep duration uninterrupted sleep regular daily sleep and wake times	Sleep: 
 
ambient light sensor: indoors, outdoors or dark location
 
ambient sound sensor: volume
 
significant motion Android software: motion leading to change in location
 
Fused Location Google API (uses GPS & wifi): location after 5 meters of movement
 
phone unlock, screen interactions and on-time duration
 
log of phone calls placed
 
log of messages sent
 
apps opened
 
app duration of use
 
	
 
Pittsburgh Sleep Quality Index Components 1, 2, 3, 6 (5 items)
 
Insomnia Problem items from the Insomnia Severity Index (3 items)
 

Sociability communication in person or in a public social environment communication with a diverse set of individuals communication with repeated partners	
 
log of phone calls placed with phone numbers
 
log of phone calls received with phone numbers
 
log of messages sent with phone numbers
 
log of messages received with phone numbers
 
social media apps opened
 
social media apps: keystrokes and duration used
 
messaging or email apps opened
 
messaging or email apps: keystrokes and duration used
 
ambient sound sensor: volume
 
Activity Recognition Google API: still, on foot
 
Fused Location Google API (by GPS & wifi): location after 5 meters of movement
 
	
 
Objective Frequency of Social Contact scale (6 items)
 
Abbreviated Lubben Social Network Scale (6 items)
 

